Patients with any of these characteristics should be excluded from the study: pregnancy or lactation, use of antibiotics in the last 3 months, phenytoin, calcium antagonists, cyclosporine or anti-inflammatory drugs one month before the initial consultation, use of oral or replacement contraceptives hormonal, periodontal treatment in the 6 months prior to the start of the study.

After being properly informed about the nature of the study, individuals must sign a free and informed consent form.

Patients will be submitted to periodontal treatment in undergraduate and graduate clinics at the UNISA Department of Dentistry, according to the needs presented.

3.3-Clinical evaluation

Patients will be evaluated by a previously trained and calibrated periodontist. Of the sample, 10% will be examined twice for each of the clinical criteria evaluated, in order to obtain the inter-examiner diagnostic reliability measured by Kappa statistics (between 0.8 and 1.0) and intra-examiner using the standard error of the measurement. (EPM). In the periodontal clinical examination, measurements will be obtained for probing depth and clinical level of insertion performed at six points per tooth: mesio buccal, labial mesio, buccal mesio, mesio lingual / palatine, lingual / palatine medium, this lingual / palatine, using periodontal probe manual (PCPUNC 15, Hu-Friedy, Chicago, USA). For Plaque Index and Gingival Index (Ainamo & Bay, 1975), dichotomous evaluation will be performed on the faces: vestibular, mesial, distal and lingual / palatal.

Patients will be observed in two stages, as shown in figure 1, prior to the start of treatment (T0) where clinical examinations will be performed, radiographs will receive dental scaling and root planing treatment (T1) and 90 days after therapy (T2) will be evaluated again (Nakamura-Minami, et al., 2003; Figueredo et al., 2004; Gomi, et al., 2007).

3.4- Physical Evaluation

The following demographic variables will be assessed: age, sex, race and education. We will adopt the following inclusion criteria: Be a practitioner of one of the modalities investigated for more than 5 years and perform more physical activity than the minimum recommendations per week, for this analysis we will use the international physical activity questionnaire.

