The evaluations performed will be: Aerobic running performance evaluation test, critical speed in swimming, body composition evaluation, muscle strength through the 1RM test in the bench press and short-term heart rate variability at rest. The evaluations proposed by the present study will be carried out in three days, with an interval of 24 hours.

Risk stratification for cardiovascular events during exercise will be performed according to the ACS recommendations. An anamnesis will be performed based on the following cardiovascular risk factors: age, family history of cardiovascular disease, smoking, high blood pressure, dyslipidemia or hypercholesterolemia, diabetes or hyperglycemia.

3.5- Periodontal Therapy

Periodontal treatment will start after physical tests of strength, speed and endurance. The individuals evaluated in this study will receive instructions on oral hygiene, including brushing technique and use of dental floss / tape, and treatment of dental scaling and root planing (RDAR).

After anamnesis, the individuals included will receive instructions for individualized oral hygiene. The treatment of RDAR will be performed in a single session (full-mouth disinfection) according to the established protocol (Quirynen et al 1999, 2006), with two sessions carried out in 24 hours.

The individuals will be treated by a single periodontist and the scraping and planing procedures will be performed on all teeth as follows: local anesthetic infiltrative type of the areas to be treated, RDAR using Gracey 5/6 carbon steel curettes, 11/12, 13/14 and MacCall 13/14, 17/18 curettes, according to their therapeutic indications. Polishing the quadrants treated with abrasive paste; oral hygiene instructions including brushing of the Bass type, dental floss and sometimes toothbrush inter dental or unitufo (Apatzidou; Riggio, Kinane, 2004, Jervoe-Stormet al., 2006).

After the dental scaling and root planing procedures, 90 days should be waited for reassessment and conducting the new clinical and physical exams. The individuals will then be referred to the clinics in operation at the Faculty of Dentistry of UNISA according to their needs.

3.6 - Statistical analysis

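### Nothing in the plan keeps T0 readings from the T2 examiner or oral findings from the physical testers, and examiner and treating periodontist are not said to differ, so expectation could shift outcomes toward benefit

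*Combined protocol and SAP*

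**What the plan says.** **Clinical examination (3.3).** "Patients will be evaluated by a previously trained and calibrated periodontist". For the pocket and attachment readings, "measurements will be obtained for probing depth and clinical level of insertion performed at six points per tooth", with a manual probe. For plaque and gingival scores, "dichotomous evaluation will be performed on the faces: vestibular, mesial, distal and lingual / palatal". The quality check is duplicate examination: "Of the sample, 10% will be examined twice for each of the clinical criteria evaluated, in order to obtain the inter-examiner diagnostic reliability", with a kappa target of 0.8 to 1.0 and an intra-examiner standard error of measurement.

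**Treatment (3.2 and 3.5).** Section 3.5 says "The individuals will be treated by a single periodontist". Section 3.2 says "Patients will be submitted to periodontal treatment in undergraduate and graduate clinics at the UNISA Department of Dentistry, according to the needs presented". Neither section says how the treating role relates to the examining role.

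**Physical tests (3.4).** Besides the aerobic running test, the battery is "critical speed in swimming, body composition evaluation, muscle strength through the 1RM test in the bench press and short-term heart rate variability at rest". The staff who run it are not identified. Section 3.5 places the baseline tests before treatment.

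**Comparison (secondary objectives, 3.1, 3.6).** Outcomes are compared before treatment and 90 days after it. No untreated or randomised comparison group is described. Section 3.6 plans ANOVA and generalized estimating equation (GEE) models relating probing depth, plaque and bleeding to the physical tests, at a 5% significance level.

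Blinding, masking, withheld T0 records and independent assessment are not mentioned anywhere. Figure 1 is not shown, but section 3.3 cites it only for the observation stages.

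**The concern.** Manual probing and yes/no plaque or bleeding scores require judgement at every site. An examiner who has the T0 chart open, or who carried out the treatment, has an expectation about the T2 reading. Running, swimming critical speed and "muscle strength through the 1RM test in the bench press" depend on effort, and effort responds to encouragement and to knowledge of the score to beat. Body composition and resting heart rate variability are much less exposed.

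In a controlled trial, drift common to both arms would largely cancel. Here there is no second arm, so any drift in assessment between T0 and T2 adds directly to the estimated change and cannot be separated from an effect of treatment. The GEE analysis has a further exposure: a tester who knew which athletes had severe disease could encourage them differently, which would distort the association between oral status and performance itself.

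**Working it through.** **Step 1: what the existing safeguards cover.**

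| Safeguard in 3.3 | What it checks | Does it limit expectation at T2? |
|---|---|---|
| Training and calibration | Agreement on how to measure | No |
| Duplicate examination of 10% (0.10 × 120 = about 12 people), kappa 0.8-1.0 | Agreement between examiners | No |
| Intra-examiner standard error of measurement | Repeatability of one examiner | No |

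An examiner can be highly repeatable within a visit and still read differently after therapy. Nothing in the plan protects the physical tests in this respect.

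**Step 2: who does what.** Section 3.3 refers to a periodontist who evaluates, and section 3.5 to one periodontist who treats. The inter-examiner statistic implies at least two examiners, if only for the duplicate subset. Section 3.2 places treatment in student clinics, which does not sit easily with a single treating periodontist. Overlap between examiner and treating periodontist is therefore possible but not stated.

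**Step 3: illustration of size.** The plan has no power calculation, effect size or SD, so there is no figure of its own to reproduce.

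Inputs:
- n = 120: the approximate number to be examined (3.1).
- n = 60: an assumption, half of 120, to allow for exclusions and 90-day losses.
- Significance level 5% (3.6); two-sided is assumed, because the plan does not say.
- Shifts and SDs of within-person change: all assumed.

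Formula (normal approximation, paired comparison, no true change): with d = (shift / SD) × √n,

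rejection rate = 1 − Φ(1.96 − d) + Φ(−1.96 − d).

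Probing depth, smallest case, n = 120: shift/SD = 0.05/0.4 = 0.125; d = 0.125 × 10.954 = 1.369; rate = 0.2774 + 0.0004 = 0.278.

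Probing depth, largest case, n = 120: shift/SD = 0.1/0.3 = 0.333; d = 3.651; rate = 0.955 (0.9546).

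| Outcome | Assumed shift | Assumed SD of change | Shift/SD | n=120 | n=60 |
|---|---|---|---|---|---|
| Probing depth | 0.05 mm | 0.4 mm | 0.125 | 27.8% | 16.2% |
| Probing depth | 0.1 mm | 0.3 mm | 0.333 | 95.5% | 73.3% |
| Effort test | 1% | 8% | 0.125 | 27.8% | 16.2% |
| Effort test | 2% | 5% | 0.400 | 99.2% | 87.3% |

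Smaller drifts matter too. At n = 120, a drift of 0.05 SD gives 8.5% and 0.10 SD gives 19.5%, against a nominal 5%. At n = 60 these are 6.7% and 12.1%.

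**The case against.** The strongest reply has four parts.

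*The rates are not specific to assessor bias.* This stands. Practice effects, regression to the mean or participant expectation of the same size would give the same figures. T2 is known to be post-treatment, so withholding charts removes only an unknown part of any shift.

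*The dominant weakness is the missing control group, and performance is only a secondary objective.* Both statements are correct. They limit how much masking can achieve, but they do not justify leaving an inexpensive safeguard out.

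*A different examiner at T2 could make matters worse.* This also stands. If one person charts T0 and another charts T2, any systematic offset between them is confounded with time and looks like a treatment effect. Kappa of 0.8-1.0 on about 12 people would not exclude a mean offset of 0.05-0.1 mm. The examiner must therefore be the same at both visits.

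*The documents do not show that bias occurs.* They do not. A reader might infer that one periodontist both treats and examines, that T0 charts are consulted at T2, or that the physical testers know who had severe disease. None of this is stated. The roles and the testers' knowledge are left open, and the point is that nothing prevents these situations.

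**Conclusion.** The concern holds as an unguarded risk, not as a demonstrated bias. The plan is silent on masking and on the separation of roles, its reliability checks address reproducibility only, and the uncontrolled before-after comparison passes any assessment drift straight into the estimated change.

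If drift occurs at the assumed sizes, the false-positive rate is about 28-95% for probing depth and 28-99% for effort-dependent tests at n=120, or 16-73% and 16-87% at n=60. These ranges show sensitivity to drift; they are not an estimate of how much drift there will be. They rest on assumed shifts and SDs, a two-sided 5% test and the normal approximation.

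The exposed outcomes are probing depth, attachment level, plaque, bleeding, running, swimming critical speed and bench-press 1RM. This is a cheap improvement worth making. It does not cure the lack of a control group.

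**What to change.** Add to sections 3.3 and 3.4:

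1. T2 is recorded on a blank chart. T0 readings and treatment notes are withheld from the examiner until the T2 data are entered.
2. Physical-test staff are not given the periodontal findings or the T0 scores, and they use one scripted instruction, including encouragement, at both visits.
3. State whether the examining periodontist is also the treating periodontist, and reconcile the descriptions of who treats in 3.2 and 3.5.
4. If a second calibrated examiner already exists, as the inter-examiner kappa suggests, the same non-treating examiner does both T0 and T2 for each participant. The examiner never changes between visits. If there is no second examiner, items 1 and 2 still apply.
5. State as limitations that the visit itself cannot be masked and that participant expectation, practice effects and regression to the mean remain.

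Cost: separate T0 and T2 forms, a script and minor logistics. Items 1 to 3 and 5 need no extra staff or procedures, and item 4 applies only where the second examiner is already in place.

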Protocol: Evaluation of oral condition and the effect of dental treatment on physical parameters of athletes

Researcher: [name]

Approval of the Research Ethics Committee in Brazil: 93416718.1.0000.0081

Approval date: 09/August/2018

Main goal

Evaluate the oral condition and propose dental treatment according to the needs of athletes linked to the Faculty of Physical Education of the Santo Amaro University.

Secondary objectives.

- Comparing the athlete's performance through physical tests of strength, speed, endurance, before and after dental treatment;
- Relate the oral conditions found with the specific habits of each sport;
- Assess the effect of biofilm control on the oral and performance conditions of the evaluated athletes.

Protocol:

This research project will comply with Resolution No. 196, of October 16, 1996, of the National Health Council, and the Dental Professional Code of Ethics (Resolution CFO No. 042/2003).

All recruited individuals will be offered verbal and written explanations of the objectives, methodology, benefits and possible risks related to participation in the project. Thus, individuals who accept to participate in the study, will sign the Free and Informed Consent Term, previously evaluated and approved by the Research Ethics Committee involving human beings of UNISA.

3.1-Experimental design

Students and / or athletes linked to the Faculty of Physical Education of the University Santo Amaro must be evaluated. According to an initial survey, about 120 individuals should be examined. Clinical parameters such as decayed, lost and / or filled dental index (CPO) and periodontal parameters such as probing depth (PS), clinical level of insertion (NCI), plaque index (IP) and bleeding index (IS) will be evaluated . Physical tests of strength, speed and resistance should be performed and periodontal therapy should be performed according to the needs presented by each individual. After 90 days, new clinical examinations and physical tests should be performed.

3.2-Selection of patients

Individuals practicing physical activities linked to UNISA will be included. Initially, we will have a convenience sample that will later be stratified into groups for evaluation and analysis. Individuals with systemic pathologies, smokers, should be included in the study

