Analysis of variance (ANOVA) will be used to compare the averages of dental clinical values and physical tests. Parametric and non-parametric values should be analyzed. The analyzes and graphs of the present study will be performed with the aid of the statistical program graphPad Prism version 4.0. The data present in the graphs will be expressed as mean \pm SEM (standard error of the mean).

With the objective of studying the association between the probing depth, presence of plaque, presence of bleeding and existence of maintenance variables, as the physical exercises performed before and after dental treatment generalized estimating equation models should be used. The score test will be used to test the target hypotheses, because the observations are dependent. The Gaussian with an identity link function will be applied. The half-normal probability plot with a simulated envelope¹⁵ made it possible to observe that the model was well adjusted. R software, version 3.2.5, will be used to analyze the data and a significance level of 5% was considered for all the tests.

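### Does section 3.6 need rewriting because its ANOVA names no within-athlete term and no unit of analysis?

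*Combined protocol and SAP*

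**What the plan says.** Section 3.6 has two analysis statements. The first is general: "Analysis of variance (ANOVA) will be used to compare the averages of dental clinical values and physical tests". It names no visits, factors or subject term, and does not say whether the averages are taken per athlete or over sites.

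The second introduces the GEE, for relating probing depth, plaque and bleeding to further variables; the clause that names the method reads "existence of maintenance variables, as the physical exercises performed before and after dental treatment generalized estimating equation models should be used". The wording is damaged, but the models have a Gaussian distribution and identity link, and the section adds: "The score test will be used to test the target hypotheses, because the observations are dependent".

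The design context is in the objectives and in sections 3.1 and 3.3. Two secondary objectives depend on change over time: comparing "performance through physical tests of strength, speed, endurance, before and after dental treatment", and "Assess the effect of biofilm control on the oral and performance conditions of the evaluated athletes". Section 3.1 expects some 120 people, lists CPO and insertion level among the oral parameters, and states "After 90 days, new clinical examinations and physical tests should be performed". It describes no untreated group. Section 3.3 takes probing depth and insertion level at six sites on each tooth, and plaque and gingival indices on four surfaces. Section 3.2 describes a convenience sample that is to be divided into strata afterwards.

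**The concern.** Oral values are dependent in two ways. Each athlete is seen before treatment (T0) and 90 days after it (T2), and each mouth supplies many sites. An ANOVA without a subject term ignores the first dependence; an ANOVA with sites as rows ignores the second. The two errors can pull in opposite directions. Unpaired athlete averages usually lose power, while independent sites can produce false positives.

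The GEE paragraph does not obviously rescue the oral measures. Its reference to before and after reads most naturally with the physical exercises, and insertion level and CPO are absent from it. For the physical tests, both methods are mentioned and neither is said to decide. With no control group, the T0-T2 change is the whole estimate for the two objectives above, so the choice of test would matter.

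**Working it through.** The plan gives no power, effect size, SD or correlation, so there is no figure of its own to reproduce. From the documents: about 120 athletes, six sites per tooth, 5% significance. Assumed: two-sided testing, complete pairs, SD of 1 at both visits, and every correlation, effect size and tooth count below.

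**1. One average per athlete, pairing ignored.** Unpaired SE = √(2/120) = 0.129, so the cut-off is 1.96 × 0.129 = 0.253. True SE = √(2(1−r)/120), which is 0.108, 0.091 and 0.071 for r = 0.3, 0.5 and 0.7.

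- Type I error = 2(1−Φ(0.253/true SE)) = 1.9%, 0.56%, 0.03%. The error is conservative for positive r. It would be 7.4% at r = −0.2.
- Power for a change δ: unpaired 1−Φ((0.253−δ)/true SE); within athlete Φ(δ/true SE−1.96).

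| δ (SD) | r | Unpaired | Within athlete |
|---|---|---|---|
| 0.2 | 0.3 | 31% | 46% |
| 0.2 | 0.5 | 28% | 59% |
| 0.2 | 0.7 | 23% | 81% |
| 0.3 | 0.5 | 70% | 91% |
| 0.4 | 0.5 | 95% | 99% |
| 0.5 | 0.5 | 99.7% | about 100% |

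In simulation at δ = 0.2 and r = 0.5, the unpaired ANOVA and the athlete-clustered GEE disagree in about 30% of studies. That figure belongs to a small effect; the power gap nearly closes by 0.4 SD.

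**2. Every site an independent row.** Assume 26 teeth × 6 = 156 sites and total variance 1, with 0.20 between athletes, s as a visit shift shared by the whole mouth, and 0.80−s at site level. The ratio of true to naive SE is R = √(156s + 0.80 − s) and the type I error is 2(1−Φ(1.96/R)).

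| s | R | Type I error |
|---|---|---|
| 0 | 0.89 | 2.8% |
| 0.01 | 1.53 | 20% |
| 0.02 | 1.97 | 32% |
| 0.05 | 2.92 | 50% |

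A second parameterisation uses 28 teeth × 6 = 168 sites and a variance ratio of (1−r)(1+167×ICC), where r is the same-site correlation and ICC the clustering of change. It gives 3% to 69% over r = 0.3 to 0.7 and ICC = 0.01 to 0.20. The inflation comes from s or the ICC, which the documents do not supply. This route also means treating 120 × 156 = 18,720 rows per visit as independent, under a section that says its observations are not.

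**3. The sensible reading.** With two visits and one value per athlete, a repeated-measures ANOVA is the paired t-test squared. With athlete as cluster, the GEE score statistic is z = Σd/√Σd². Since Σd² = (n−1)s_d² + n·d̄², it follows that z² = n·t²/(n−1+t²), so the two statistics rank data sets identically. At n = 120 the t cut-off of 1.980 corresponds to z = √(120 × 3.921/(119 + 3.921)) = 1.956, against 1.960 for the score test. In simulation the two verdicts differ in at most 0.2% of studies.

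**4. The text again.** The ANOVA sentence mentions neither visit. It can be read as a repeated-measures comparison, or as a comparison of the strata foreseen in section 3.2, where a between-group ANOVA of athlete averages at one visit needs no within-athlete term.

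**The case for a change.** The best case for requiring a change is that two analysts following section 3.6 could run different tests, with errors in opposite directions. Even a generous reading of the GEE sentence, covering change in probing depth, plaque and bleeding, leaves insertion level and CPO out. If the ANOVA is meant for the strata, those two have no before-after test at all. A few words would settle it, with no new data.

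Much of this stands as description. The type of ANOVA, the unit of analysis and the deciding method are unstated, and the arithmetic is right under its assumptions. What does not follow is that the plan specifies a faulty analysis. Two measurements on the same athlete lead naturally to a within-athlete comparison, and section 3.6 shows that its authors know the data are dependent.

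The exposed measures are also fewer than they seem. CPO is an index of decayed, lost or filled teeth, so the site-level scenario does not reach it. The therapy in section 3.5 is hygiene instruction with scaling and root planing, referral for other needs follows reassessment, and no objective names a 90-day CPO change. Plaque and bleeding are described as indices too, so the site-level scenario bears mainly on probing depth and insertion level.

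Finally, making the GEE decide every T0-T2 comparison would widen its stated purpose, which is association, and demote a repeated-measures ANOVA that performs equally well. That is a preference between methods.

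**Conclusion.** No change to the plan follows. Section 3.6 is thin here, but the gap is one that a competent analyst fills correctly by using one value per athlete per visit and comparing within athlete. On that reading, repeated-measures ANOVA and the planned GEE clustered on athlete agree in more than 99% of simulated studies.

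The losses computed above need a poor choice that the text does not ask for. Unpaired athlete averages are conservative at any positive correlation, and at r = 0.5 cost 31 percentage points of power at 0.2 SD (59−28) but only about 4 at 0.4 SD (99−95). False positives of 20% to 50% need both sites treated as independent and an assumed shared visit shift; without the shift the figure is 2.8%. The two sets of assumptions do not describe the same data either. The site model implies athlete-average correlations of 0.20/(0.20 + s + (0.80−s)/156), which run from 0.975 at s = 0 to 0.78 at s = 0.05, outside the 0.3 to 0.7 used for athlete averages.

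The point concerns secondary objectives; the main goal is to evaluate oral condition and propose treatment. The conclusion rests on reading the ANOVA sentence as silent about pairing, not as excluding it. It would change if the documents stated that sites were to be analysed as independent observations, or that T0 and T2 were to be treated as separate samples. They state neither.

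### Section 3.6 does not separate between-athlete from within-athlete association in the GEE; if each oral measure gets one coefficient, that slope mixes the two.

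*Combined protocol and SAP*

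**What the plan says.** Section 3.6 (Statistical analysis) gives the comparison of mean dental and physical values to ANOVA. It then plans a second analysis of the "association between the probing depth, presence of plaque, presence of bleeding and existence of maintenance variables" with the physical tests: "as the physical exercises performed before and after dental treatment generalized estimating equation models should be used". The remaining details are "The Gaussian with an identity link function will be applied", "The score test will be used to test the target hypotheses, because the observations are dependent", and "a significance level of 5% was considered for all the tests".

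Oral and physical measures are taken before therapy and again at follow-up (section 3.1: "After 90 days, new clinical examinations and physical tests should be performed"). The expected size is also in 3.1: "According to an initial survey, about 120 individuals should be examined". The objective that this model would most naturally inform is the third secondary one: "Assess the effect of biofilm control on the oral and performance conditions of the evaluated athletes".

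The text does not say:
- how the oral variables are coded, or whether they are reduced to one value per athlete and visit;
- which side of the model is the response;
- what the working correlation is;
- whether there is a visit term.

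No change score, baseline adjustment or split into athlete mean and deviation appears anywhere.

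**The concern.** Probing depth, plaque and bleeding differ between athletes and also change from T0 to T2. With a single coefficient, such a variable answers two questions at once: whether athletes with cleaner mouths perform better, and whether an athlete whose plaque falls then improves. Only the second bears on biofilm control.

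A stable trait such as general self-care or discipline could drive both hygiene and fitness. It would produce a between-athlete slope even if the within-athlete slope were zero. A visit term does not remove this, because the trait does not change between visits, and adjustment for measured covariates cannot fully remove an unmeasured trait. Using GEE because observations are dependent corrects the variance but does not change what the slope estimates. The risk is that a significant pooled slope is read as support for an effect of oral care on performance.

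**Working it through.** The plan gives no effect size, power or correlation figure, so there is nothing of its own to reproduce.

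**Inputs from the documents.** About 120 athletes, two measured occasions, Gaussian identity GEE, score test, 5% level (two-sided assumed).

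**Assumed inputs.** Oral T0–T2 correlation rx, performance correlation ρ, and correlation c between an athlete's stable oral level and stable performance level. Both variables have SD 1, and the true within-athlete slope is zero.

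**Step 1: weight on the within-athlete slope (visit term in the model).**
- Independence: w = (1 − rx)/2.
- Exchangeable: w = a/(a + b), with a = (1 − rx)/(1 − ρ) and b = (1 + rx)/(1 + ρ).

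| rx | Independence | Exchangeable, ρ = 0.5 / 0.8 / 0.9 |
|---|---|---|
| 0.3 | 0.35 | 0.62 / 0.83 / 0.91 |
| 0.5 | 0.25 | 0.50 / 0.75 / 0.86 |
| 0.7 | 0.15 | 0.35 / 0.61 / 0.77 |

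**Step 2: expected slope at rx = 0.5, ρ = 0.85, c = 0.3.** The covariance of the stable parts is 0.3 × √(0.5 × 0.85) = 0.196. The between-athlete slope is 0.196 / [(1 + 0.5)/2] = 0.261.
- Independence: (1 − 0.25) × 0.261 = 0.196.
- Exchangeable: a = 0.5/0.15 = 3.33, b = 1.5/1.85 = 0.81, w = 0.80; slope (1 − 0.804) × 0.261 = 0.051.
- Within-athlete: 0.

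**Step 3: hand check of the rejection rate, N = 120.**
- Independence: SE ≈ √[(1 + 0.5 × 0.85)/(2 × 120)] = √0.00594 = 0.077; z ≈ 0.196/0.077 = 2.54; rejection ≈ Φ(2.54 − 1.96) = 72%.
- Exchangeable: SE ≈ 1/√[120 × (3.33 + 0.81)] = 0.045; z ≈ 0.051/0.045 = 1.14; rejection ≈ Φ(1.14 − 1.96) = 21%.

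**Step 4: simulation at the same values, visit term included.** Ranges cover a sandwich-variance test (2,000 runs) and the generalized score test (4,000 runs). The c = 0 row is the score test only.

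| c | One slope, independence | One slope, exchangeable | Change on change |
|---|---|---|---|
| 0 | 5.3% | 5.0% | 4.7% |
| 0.2 | 38–40% | 12–14% | 4.8–5.3% |
| 0.3 | 71–73% | 19–22% | 3.8–5.3% |
| 0.4 | 92–93% | 33–34% | 4.6–5.3% |

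**Step 5: other assumptions.** These runs used oral correlation 0.6, an oral fall of 0.5 SD, performance correlation 0.7 or 0.9, the score test and 1,000 runs per setting. At a stable-trait correlation of 0.3 in absolute value, with a visit term, one slope rejects in 71–78% (independence) and 22–36% (exchangeable) at N = 120. At N = 60 the figures are 41–46% and 12–20%. The deviation term rejects in 3.5–5.7% at N = 120 and 3.2–6.0% at N = 60 when performance has no average drift.

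**Step 6: the split also needs a visit term.** Suppose performance (correlation 0.9) rises by 0.1 or 0.2 SD for reasons unrelated to oral change. The deviation term without a visit term then rejects in 21% or 62% of runs. With a visit term it rejects in 5.5% or 4.6%.

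**The case against.** The strongest reply is that the plan is silent rather than wrong. A reader might infer from 3.6 that each oral variable is entered as one raw value per visit. That is the default reading, but it is not stated. Section 3.3 records probing depth at six sites on each tooth and scores plaque and gingival status by tooth face, so a site-level model, or one with oral measures as the response, remains possible. The two-visit algebra above would not then apply as written. This stands, and it makes the point conditional. It does not remove the point, because the text fully permits the mixed slope.

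A reader might also extend the point to the first secondary objective. That objective compares performance before and after treatment and asks for no slope on oral change; 3.6 gives comparisons of means to ANOVA. Nor should the point cover the maintenance variable, which need not vary by visit.

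It is also fair that 3.6 describes the GEE as a study of association and claims no effect. The difficulty arises if its slope is used for the third objective, whose wording is about an effect.

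Finally, the size rests wholly on assumed correlations. The larger figures need an independence working correlation. Under an exchangeable one at the values used, about 80% of the weight is already within-athlete. With unrelated stable levels there is no inflation.

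**Conclusion.** The point holds in conditional form. Section 3.6 does not separate the two kinds of association, and if athlete-level T0 and T2 values enter with one coefficient each, the slope mixes them. With a zero within-athlete slope and the stated assumptions, false support for a link with oral change ranges from the nominal 5% (no stable-trait correlation) to about 38–93% under independence and 12–34% under an exchangeable structure (stable-trait correlation 0.2–0.4). The unstated working correlation therefore matters a good deal.

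The consequence is limited to what may be said under the third secondary objective. The documents do not support a claim that the plan has chosen a wrong coding. Nor would the within-athlete slope establish an effect: no control arm is described, so changes in training or season that differ by athlete could still move hygiene and performance together.

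**What to change.** In 3.6:

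1. Summarise probing depth, plaque and bleeding to one value per athlete and visit, and state the summary.
2. Make the physical test the response. Enter each of these measures as two terms: the athlete's mean over T0 and T2, and the visit's deviation from that mean.
3. Include a visit term and name the working correlation.
4. Base any statement about oral change and performance on the deviation term. Report the mean term as a cross-sectional association.
5. State that the deviation term removes stable-trait confounding only and remains associational.

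For athletes with both visits, the deviation term with a visit term is the same as regressing T2 − T0 performance change on T2 − T0 oral change. The visit term absorbs the average change, so the deviation term asks whether athletes whose mouths improved more also gained more. The average change stays with the before/after comparison.

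The cost is a few lines of text and code on measurements already planned. The within-athlete term uses less of the variation, so its interval can be wider than that of the pooled slope.
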